8.2 Determination of Sample Size

It is planned to enroll approximately 330 adult subjects with chronic HCV GT 1 - 6 infection with compensated cirrhosis who are HCV treatment-naïve in the study.

The study was initially designed to enroll about 270 non-GT3-infected subjects and amended to include GT3-infected subjects for a total of 330 GT1 - 6-infected (270 non-GT3 and 60 GT3) subjects.

With approximately 270 subjects with HCV GT1, 2, 4, 5, or 6 infection, this study has approximately 91% power to demonstrate efficacy of the 8-week treatment arm compared to the historical control SVR₁₂ rate (i.e., a two-sided 95% lower confidence bound above 94%) based on Per-Protocol (PP) population, assuming that 98% of the GT1, 2, 4, 5, and 6-infected subjects receiving 8 weeks of treatment in PP population achieve SVR₁₂.

With approximately 270 subjects with HCV GT1, 2, 4, 5, or 6 infection, this study has approximately 82% power to demonstrate efficacy of the 8-week treatment arm compared to the historical control SVR₁₂ rate (i.e., a two-sided 95% lower confidence bound above 93%) based on Intention-to-Treat (ITT) population, assuming that 97% of the GT1, 2, 4, 5, and 6-infected subjects receiving 8 weeks of treatment in ITT population achieve SVR₁₂.

With approximately 330 subjects with HCV GT1 - 6 infection, this study has approximately 90% power to demonstrate efficacy of the 8-week treatment arm compared to the historical control SVR₁₂ rate (i.e., a two-sided 95% lower confidence bound above 94%) based on the PP population, assuming that 98% of the GT1 - 6-infected subjects receiving 8 weeks of treatment in the PP population achieve SVR₁₂.

With approximately 330 subjects with HCV GT1-6 infection, this study has approximately 81% power to demonstrate efficacy of the 8-week treatment arm compared to the historical control SVR₁₂ rate (i.e., a two-sided 95% lower confidence bound above 93%) based on the ITT population, assuming that 97% of the GT1 - 6-infected subjects receiving 8 weeks of treatment in the ITT population achieve SVR₁₂.

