To determine the likelihood of success for Study M16-135, HCV modeling simulations were conducted using a viral dynamic model, including dynamics of hepatocytes, infected cells, wild type virus and mutants. In vitro efficacy and resistance data was incorporated. Viral load and SVR data from GLE/PIB Phase 2 and 3 studies in non-cirrhotic and cirrhotic subjects receiving 8 to 16 week treatment durations were included in the modeling. Additional internal and external efficacy data from treatments with different durations (4 to 24 weeks) were also taken into considerations in the modeling and simulations.

For this analysis, HCV virus in treatment-naïve GT 1, 2, 4, 5 or 6 cirrhotic subjects were assumed to have comparable responses to the GLE/PIB combination and non-virologic failures were not accounted in the simulations. The clinical trial simulation scenarios for an 8-week treatment duration in treatment-naïve subjects with compensated cirrhosis resulted in an SVR₁₂ rate of approximately 98% in GT 1-, 2-, 4-, 5-, or 6-infected subjects and approximately 92% for GT3-infected subjects.

The objectives of this study are to evaluate the efficacy and safety of 8 weeks of GLE/PIB for the treatment of treatment-naïve subjects with chronic HCV GT 1 - 6 infection and compensated cirrhosis.

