5.6.4.2 GLE and PIB Dose and Treatment Duration

GLE/PIB 300 mg/120 mg QD regimens with 8-week and 12-week durations were evaluated in non-cirrhotic subjects in registrational trials. Efficacy of 8-week treatment duration is established for GT1-, GT2- and GT3- infected non-cirrhotic subjects [R&D/16/0144, R&D/15/1230]. Fifty-two non-cirrhotic GTs 4, 5, or 6-infected subjects received 8-weeks of GLE/PIB and no virologic failure was observed. Overall, these results conclude that 8-weeks of GLE/PIB 300 mg/120 mg dose is efficacious for non-cirrhotic GT 1 - 6-infected subjects.

Based on modeling and simulations, assuming no subjects experience non-virologic failures, following 8 weeks of GLE/PIB in treatment-naïve HCV-infected subjects with compensated cirrhosis, the predicted SVR₁₂ rate is approximately 98% for GT1, 2, 4, 5, and 6-infected subjects, and approximately 92% for GT3-infected subjects.

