### **4.0 Study Objectives, Design and Procedures**

#### **4.1 Objectives**

The primary objectives of this study are to compare the SVR12 rates (12-week sustained virologic response, SVR12 [HCV ribonucleic acid {RNA} < lower limit of quantification {LLOQ} 12 weeks following treatment]) of 8 weeks of treatment with the GLE/PIB combination regimen to the historical SVR12 rate of 12 weeks of treatment with GLE/PIB in treatment naïve adults with chronic HCV infection and compensated cirrhosis and to assess the safety of 8 weeks of treatment with the GLE/PIB combination regimen in treatment naïve adults with chronic HCV infection and compensated cirrhosis.

The secondary objectives of this study are to assess the percentage of subjects with on-treatment virologic failure and the percentage of subjects with post-treatment relapse.

to the historical control SVR12 rate (i.e., a two-sided 95% lower confidence bound above 94%) based on the Per-Protocol (PP) population, assuming that 98% of the GT1, 2, 4, 5, and 6-infected subjects receiving 8 weeks of treatment in the PP population achieve SVR12.

With approximately 270 subjects with HCV GT 1, 2, 4, 5, or 6 infection, this study has approximately 82% power to demonstrate efficacy of the 8-week treatment arm compared to the historical control SVR12 rate (i.e., a two-sided 95% lower confidence bound above 93%) based on the ITT population, assuming that 97% of the GT1, 2, 4, 5, and 6-infected subjects receiving 8 weeks of treatment in the ITT population achieve SVR12.

With approximately 330 subjects with HCV GT 1 - 6 infection, this study has approximately 90% power to demonstrate efficacy of the 8-week treatment arm compared to the historical control SVR12 rate (i.e., a two-sided 95% lower confidence bound above 94%) based on the PP population, assuming that 98% of the GT1 - 6-infected subjects receiving 8 weeks of treatment in the PP population achieve SVR12.

With approximately 330 subjects with HCV GT 1 - 6 infection, this study has approximately 81% power to demonstrate efficacy of the 8-week treatment arm compared to the historical control SVR12 rate (i.e., a two-sided 95% lower confidence bound above 93%) based on the ITT population, assuming that 97% of the GT1 - 6-infected subjects receiving 8 weeks of treatment in the ITT population achieve SVR12.

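### The 90% and 81% power stated for the two GT1-6 key secondary tests do not follow from the stated assumptions, and the pooled response rate leaves out the protocol's own 92% prediction for GT3

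*Protocol*

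**What the plan says.** Protocol 8.2 plans "for a total of 330 GT1 - 6-infected (270 non-GT3 and 60 GT3) subjects". It gives four power statements:

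- 270 non-GT3, PP, 98% assumed: about 91%.
- 270 non-GT3, ITT, 97% assumed: about 82%.
- 330 GT1-6, PP, 98% assumed: "this study has approximately 90% power to demonstrate efficacy of the 8-week treatment arm compared to the historical control" rate.
- 330 GT1-6, ITT, 97% assumed: "approximately 81% power to demonstrate efficacy of the 8-week treatment arm".

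Success needs "a two-sided 95% lower confidence bound above 94" percent for PP and "a two-sided 95% lower confidence bound above 93" percent for ITT, in both groups. SAP 4.3 (Sample Size) repeats the GT1-6 statement of "approximately 90% power to demonstrate efficacy of the 8-week treatment arm compared" to the historical rate, and the 81%.

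Protocol 5.6.4.2 gives the model prediction for 8 weeks in treatment-naïve subjects with compensated cirrhosis, before non-virologic failures: "approximately 98% for GT1, 2, 4, 5, and 6-infected subjects, and approximately 92% for GT3-infected subjects". The modelling part of Protocol 3.0 gives the same GT3 figure, "approximately 92% for GT3-infected subjects".

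Protocol 8.1.2.1 and SAP 10.3 set the interval for the primary tests: normal approximation (Wald), replaced by Wilson's score when there are fewer than 5 failures. The protocol synopsis applies this rule to the key secondary tests too. Wilson for all cases is a sensitivity analysis (Protocol 8.1.2.3, SAP 10.5). Protocol 8.1.2.6 and SAP 10.2 fix the order: PP non-GT3, ITT non-GT3, PP GT1-6, ITT GT1-6.

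**The concern.** Two things do not fit.

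First, with the same true rate, threshold and confidence level, stand-alone power should not fall when 60 subjects are added. Section 8.2 has it falling from 91% to 90% and from 82% to 81%, without saying that the GT1-6 figures mean anything other than stand-alone power.

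Second, if 270 non-GT3 subjects respond at 98% and the pooled 330 also respond at 98%, the 60 GT3 subjects must respond at 98% (and at 97% in ITT). The model's 98% for non-GT3 equals the planning rate, but its 92% for GT3 is not carried into the pooled rate, and section 8.2 does not say why.

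At stake is whether a reader of the protocol or SAP can tell how likely the amended trial is to support its GT1-6 claim.

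**Working it through.** **Inputs.** n = 270 and 60; rates 98% (PP) and 97% (ITT); thresholds 94% and 93%; two-sided 95% interval (Protocol 8.2). GT3 prediction 92% (Protocol 3.0 and 5.6.4.2). Non-virologic failure allowance 1% (Protocol 8.2.1), which gives a derived GT3 ITT rate of 92% − 1% = 91%.

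**1. Reproduce the 270-subject figures.** Normal approximation with the null variance:

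power = Φ{[(p1 − p0) − 1.96·√(p0(1−p0)/n)] / √(p1(1−p1)/n)}

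- PP: (0.04 − 0.02833)/0.00852 = 1.37, so 91.5% (stated 91%).
- ITT: (0.04 − 0.03043)/0.01038 = 0.92, so 82.2% (stated 82%).

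**2. Same formula at 330.**

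- PP: (0.04 − 0.02562)/0.00771 = 1.87, so 96.9% (stated 90%).
- ITT: (0.04 − 0.02753)/0.00939 = 1.33, so 90.8% (stated 81%).

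**3. Planned interval rule at 330, exact binomial.** At most 12 failures pass in PP (318/330, lower bound 94.3%; 13 failures give 93.96%). At most 15 pass in ITT (315/330, lower bound 93.2%; 16 give 92.8%). Both counts exceed 4, so Wald applies at the cut-off.

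- PP: P(Bin(330, 0.02) ≤ 12) = 98.3%.
- ITT: P(Bin(330, 0.03) ≤ 15) = 95.7%.

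**4. Where 90% and 81% may come from.** The probability of passing the test at 270 and again at 330 in the same population, at equal rates, is 90.1% (PP) and 80.4% (ITT) by exact Wilson, and 91.2% and 81.3% by the normal approximation. That is the nearest match. It is an inference: neither document labels the figures as joint. It also leaves out the ITT non-GT3 test, which stands between the two PP tests.

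**5. Put the model's GT3 rate in.**

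- Pooled PP rate: (270 × 0.98 + 60 × 0.92)/330 = 96.9%. Expected failures 5.4 + 4.8 = 10.2, against a limit of 12.
- Pooled ITT rate: (270 × 0.97 + 60 × 0.91)/330 = 95.9%. Expected failures 8.1 + 5.4 = 13.5, against a limit of 15.

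Exact power comes from summing the two binomials. Power through all four tests was simulated with virologic failure of 2% (non-GT3) and 8% (GT3), plus 1% non-virologic failure.

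| Interval | Basis | PP | ITT |
|---|---|---|---|
| Planned Wald/Wilson rule | stand-alone | 77.7% | 72.2% |
| Planned Wald/Wilson rule | full sequence | about 76% | about 69% |
| Wilson (sensitivity method) | stand-alone | 67.6% | 62.5% |
| Wilson (sensitivity method) | full sequence | about 62% | about 56% |

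The sequential figures move by about one point with the way the 1% is combined with virologic failure.

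**6. Sensitivity to the GT3 rate (planned rule, stand-alone).** 92%/91%: 78% and 72%. 95%/94%: 92% and 87%. 98%/97%: 98% and 96%. At 98%/97%, power through the full sequence is about 92% for each test.

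**The case against.** The best defence has four parts.

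- **The figures may be joint power.** Section 8.2 never calls them stand-alone. With GT3 at 98%/97%, the planned rule gives about 92% for both tests through the full sequence, so 90% and 81% would be cautious. This stands as far as it goes. But the text does not say joint, the joint reading skips a test, and it still depends on GT3 matching the other genotypes.
- **Observed GT3 data are better than the model.** Protocol 5.6.3 cites 64/64 in PP for cirrhotic subjects at 12 weeks and 177/182 (97.3%) for non-cirrhotic subjects at 8 weeks. At 97.3%, PP power under the planned rule is 97.4%; at the observed non-cirrhotic ITT rate of 95.2% (177/186), ITT power is 91.2%. Neither data set is 8 weeks in cirrhosis, and section 8.2 cites neither. This supports a range, not silence about the 92%.
- **92% is not quite a PP rate.** The model leaves out only non-virologic failures, while the PP population also excludes breakthrough. The GT3 PP rate implied by the model is therefore 92% or a little higher, and 78% is slightly pessimistic.
- **Only secondary tests are touched.** This is correct. The primary tests, type I error and thresholds are unaffected, and GT3 response is also reported separately.

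A reader might go further and put the true power at 56% to 78%. That range mixes two endpoints, stand-alone and sequential power, and two interval methods; its lower end rests on Wilson, which is not the planned primary interval. A reader might also infer that GT3 was added because of the stated power. Protocol 5.6.3 gives registrational clinical data as the reason.

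**Conclusion.** The two GT1-6 power statements are wrong as stand-alone power on their own assumptions: about 97% and 91% by the formula that reproduces the 270-subject figures, or 98% and 96% under the planned rule, against 90% and 81% printed. Separately, the pooled rate is not reconciled with the protocol's 92% for GT3. Taking that prediction, power under the planned rule is about 78% (PP) and 72% (ITT) alone, some 12 and 9 points below the printed figures, and about 76% and 69% through the sequence.

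This rests on non-GT3 at 98%/97%, all 270 and 60 subjects enrolled, and a GT3 ITT rate of 91% that is derived, not stated. The shortfall depends on the GT3 rate: at 95%/94% stand-alone power is already above the printed figures. The documents therefore do not show that the trial is underpowered, or that 92% is the right planning rate. They show that the stated figures cannot be relied on as written.

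**What to change.** In Protocol 8.2 and SAP 4.3, replace the two GT1-6 power statements with figures for 270 non-GT3 subjects at 98%/97% plus 60 GT3 subjects over a stated range of GT3 rates (PP/ITT), computed with the planned Wald/Wilson rule:

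- 92%/91% (the model): about 78% and 72% stand-alone; about 76% and 69% through the full sequence.
- 95%/94%: about 92% and 87% stand-alone.
- 98%/97%: about 98% and 96% stand-alone; about 92% and 92% through the full sequence.

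Label each figure as stand-alone or through all four tests, and add a sentence on why the sponsor plans on a given GT3 rate in view of the model and the data in Protocol 5.6.3.

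The change is to text only. Sample size, thresholds, test order and the primary analyses stay as they are. The cost is that the stated power may look less favourable at the lower GT3 rates.

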8.2.1 Justification of Success Criteria for SVR₁₂

Efficacy for the 8-week regimen in this study is established by comparing the SVR₁₂ rate from this study to the historical control regimen of GLE/PIB administered for 12 weeks.

The SVR₁₂ rate of the historical control regimen is calculated, and a threshold is determined by subtracting a margin of 6% from the historical SVR₁₂ rate. Efficacy is established if the lower 95% confidence bound of the SVR₁₂ rate in the 8-week regimen is greater than the threshold.

In the registrational program, 117 treatment naïve, compensated cirrhotic subjects, GT 1, 2, 4, 5, or 6 subjects and 65 treatment naïve, GT3-infected subjects with compensated cirrhosis were treated with GLE/PIB for 12 weeks duration. Three subjects did not achieve SVR₁₂, one discontinued treatment early and two had missing SVR₁₂ data. No virologic failure was observed among these subjects which means SVR₁₂ rate based on PP population is 100%. Hence, for this study it assumed that the historical SVR₁₂ rate for GT1 - 6-infected cirrhotic patients is 100%. To establish efficacy to the historical control, a margin of 6% is applied to the historical control rate of 100%, resulting in a threshold of 94%.

Historical SVR rate based on ITT population depends on the non-virologic failure in a study. Study-to-study variability has been observed in non-virologic failure rates, and is typically around 1%. The observed rate of non-virologic failure in the registrational program is 1.2% (29/2369). For this reason, this study assumes that the historical SVR₁₂ rate based on ITT population for cirrhotic patients is 99% (with 1% non virologic failure). To establish efficacy to the historical control, a margin of 6% is applied to the historical control rate of 99%, resulting in a threshold of 93%.

A margin of 6% is selected to be used in this study to ensure a minimal loss of efficacy of the 8-week arm relative to the historical SVR₁₂ rate for 12-week arm.

8.3 Randomization Methods

This study is not randomized. Eligible subjects will be enrolled into a single arm.

9.0 Ethics**9.1 Independent Ethics Committee (IEC) or Institutional Review Board (IRB)**

Good Clinical Practice (GCP) requires that the clinical protocol, any protocol amendments, the Investigator's Brochure, the informed consent and all other forms of subject information related to the study (e.g., advertisements used to recruit subjects) and any other necessary documents be reviewed by an IEC/IRB. The IEC/IRB will review the ethical, scientific and medical appropriateness of the study before it is conducted. IEC/IRB approval of the protocol, informed consent and subject information and/or advertising, as relevant, will be obtained prior to the authorization of drug shipment to a study site.

Any amendments to the protocol will require IEC/IRB approval prior to implementation of any changes made to the study design. The investigator will be required to submit, maintain and archive study essential documents according to ICH GCP and all other applicable regulatory requirements.

Any serious adverse events that meet the reporting criteria, as dictated by local regulations, will be reported to both responsible Ethics Committees and Regulatory Agencies, as required by local regulations. During the conduct of the study, the investigator should promptly provide written reports (e.g., ICH Expedited Reports, and any additional reports required by local regulations) to the IEC/IRB of any changes that affect the conduct of the study and/or increase the risk to subjects. Written documentation of the submission to the IEC/IRB should also be provided to AbbVie.

9.2 Ethical Conduct of the Study

The study will be conducted in accordance with the protocol, International Conference on Harmonization (ICH) guidelines, applicable regulations and guidelines governing clinical study conduct and the ethical principles that have their origin in the Declaration of Helsinki. Responsibilities of the clinical investigator are specified in [Appendix A](#).

9.3**Subject Information and Consent**

The investigator or his/her representative will explain the nature of the study to the subject, and answer all questions regarding this study. Prior to any study-related screening procedures being performed on the subject, the informed consent statement will be reviewed and signed and dated by the subject, the person who administered the informed consent, and any other signatories according to local requirements. A copy of the informed consent form will be given to the subject and the original will be placed in the subject's medical record. An entry must also be made in the subject's dated source documents to confirm that informed consent was obtained prior to any study-related procedures and that the subject received a signed copy.

Information regarding incentives for subjects and information regarding provisions for treating and/or compensating subjects who are harmed as a consequence of participation in the study can be found in the informed consent form.

An informed consent, approved by an IRB/IEC, must be voluntarily signed and dated before samples are collected and testing performed for optional pharmacogenetic exploratory research. The nature of the testing should be explained and the subject given an opportunity to ask questions. If the subject does not consent to provide samples for the optional pharmacogenetic exploratory research, it will not impact their participation in the study.

In the event a subject withdraws from the main study, optional pharmacogenetic exploratory research samples will continue to be stored and analyzed unless the subject specifically withdraws consent for the optional samples. If consent is withdrawn for the optional sampling, the subject must inform their study doctor, and once AbbVie is informed, the optional samples will be destroyed. However, if the subject withdraws his/her consent and the samples have already been tested, those results will still remain as part of the overall research data.

10.0 Source Documents and Case Report Form Completion

10.1 Source Documents

Source documents are defined as original documents, data and records. This may include hospital records, clinical and office charts, laboratory data/information, subjects' diaries or evaluation checklists, pharmacy dispensing and other records, recorded data from automated instruments, microfiches, photographic negatives, microfilm or magnetic media, and/or x-rays. Data collected during this study must be recorded to the appropriate source document. The Investigator Awareness Date (SAE CRF) may serve as the source for this data point. This adverse event data point required for eCRF completion can be entered directly in the eCRF.

The investigator(s)/institution(s) will permit study-related monitoring, audits, IEC/IRB review, and regulatory inspection(s), providing direct access to source data documents.

10.2 Case Report Forms

Case report forms (CRF) must be completed for each subject screened/enrolled in this study. These forms will be used to transmit information collected during the study to AbbVie and regulatory authorities, as applicable. The CRF data for this study are being collected with an electronic data capture (EDC) system called Rave® provided by the technology vendor Medidata Solutions Incorporated, NY, USA. The EDC system and the study-specific electronic case report forms (eCRFs) will comply with Title 21 CFR Part 11. The documentation related to the validation of the EDC system is available through the vendor, Medidata, while the validation of the study-specific eCRFs will be conducted by AbbVie and will be maintained in the Trial Master File at AbbVie.

The investigator will document subject data in his/her own subject files. These subject files will serve as source data for the study. All eCRF data required by this protocol will be recorded by investigative site personnel in the EDC system. All data entered into the eCRF will be supported by source documentation.

The investigator or an authorized member of the investigator's staff will make any necessary corrections to the eCRF. All change information, including the date and person performing the corrections, will be available via the audit trail, which is part of the EDC system. For any correction, a reason for the alteration will be provided. The eCRFs will be reviewed periodically for completeness, legibility, and acceptability by AbbVie personnel (or their representatives). AbbVie (or their representatives) will also be allowed access to all source documents pertinent to the study in order to verify eCRF entries. The principal investigator will review the eCRFs for completeness and accuracy and provide his or her electronic signature and date to eCRFs as evidence thereof.

Medidata will provide access to the EDC system for the duration of the trial through a password-protected method of internet access. Such access will be removed from investigator sites at the end of the site's participation in the study. Data from the EDC system will be archived on appropriate data media (CD-ROM, etc.) and provided to the investigator at that time as a durable record of the site's eCRF data. It will be possible for the investigator to make paper printouts from that media.

